2.3 CLINICAL STUDIES

NGM has conducted a Phase 1 clinical trial in normal volunteers as well as Phase 2a and 2b trials in PBC patients. These studies are supportive of the clinical development of NGM282 in patients with PSC. Please refer to the IB for additional detailed information on these studies.

2.4 RATIONALE FOR DOSE SELECTION OF NGM282 FOR PSC

The doses selected for the Phase 2 trial in PSC are supported by both the nonclinical and clinical data generated to date. The dose range for the first-in-human Phase 1 clinical trial (0.1–30 mg) was based on a broad approach to dose calculation considering the pharmacology of FGF19, beyond sole reliance on the NOAEL obtained in the GLP 28-day toxicology program. The dose range also took into consideration safe starting-dose principles for first-in-human administration as outlined in both FDA and CHMP guidance. Dose-proportional changes in pharmacokinetic (PK) parameters were observed with both single and multiple dosing in the Phase 1 trial, consistent with predictions from animal models. All doses were safe and well tolerated, thus establishing the initial clinical safety of this dose range.

The proposed doses of 1 and 3 mg for evaluation in patients with PSC are based on a cumulative broad approach to dose calculation considering the pharmacology of FGF19 in PSC, clinical data from normal volunteers and subjects with PBC, and exposure safety margins obtained in the GLP 26-week toxicology program relative to the clinical doses proposed. The proposed doses of 1 and 3 mg are within the current safety margins in both monkeys and mice ([Table 2.2.1-1](#)). The drug exposure is comparable between normal volunteers and all populations studied to date (type 2 diabetes [T2D], PBC) and, therefore, expected to be comparable in the PSC population.

The selection of the 1- and 3-mg doses was based on the efficacy, safety, and tolerability observed in the PBC Phase 2a trial in which NGM282 doses of 0.3 and 3 mg were evaluated.

A total of 45 patients were enrolled and randomized into the three study arms of 0.3 mg (n=14), 3.0 mg (n=16), or placebo (n=15). A progressive and statistically significant decrease in mean absolute ALP from Baseline to Day 28 was noted in both active treatment groups (p<0.025). A dose-related response was observed in absolute change in ALP from Baseline to the respective visits, with greater decreases in ALP shown with the higher (3.0 mg) dose of NGM282 (absolute change from Baseline to Day 28: -48.9 IU/L in the 0.3-mg group, -69.0 IU/L in the 3.0-mg group, and 3.9 IU/L in the placebo group). Statistically significant overall treatment effects were demonstrated for both 0.3-mg and 3.0-mg doses for alanine aminotransferase (ALT) and aspartate aminotransferase (AST) whereas only for the 3.0-mg dose for GGT and serum C4 levels. The majority of the treatment-emergent adverse events (TEAEs) reported in this study were either mild or moderate in intensity. The frequency of related TEAEs was slightly higher in the 3.0-mg treatment group compared to the other two treatment groups. Diarrhea was the most frequently reported and treatment-related TEAE; 3 of 14 subjects (21.4%) in the 0.3-mg group reported three events, 4 of 16 subjects (25.0%) in the 3.0-mg group reported six events, and 1 of 15 subjects (6.7%) in the placebo group reported two events. Overall, the study drug was well tolerated by the subjects. The majority of subjects in all treatment groups reported “no reaction” to the injection site. Of those reported, all but one were mild and predominantly reported as erythema at the injection site. No evidence of drug-induced pruritus was observed, as assessed through both the Visual Analogue Scale and the 5D Pruritus Scale. In summary, NGM282 demonstrated significant reductions in key markers of hepatobiliary injury and has a favorable safety and tolerability profile in PBC patients treated for 28 days.

The PBC study subjects represent a population similar to the PSC population based on the underlying role of bile acids in the associated inflammation and hepatobiliary injury. Based on the above data, the selected doses should allow a balance of optimizing the biologic activity versus safety and tolerability in the studied population.

3 STUDY OBJECTIVES

Primary Objective:

- Evaluate the treatment effect of NGM282 as measured by the mean change in ALP from Baseline to Week 12 in patients with PSC.

Secondary Objectives:

- Assess the safety and tolerability of NGM282 in patients with PSC with 12 weeks of treatment.
- Evaluate the percentage change from Baseline at Week 12 in ALP.
- Evaluate the absolute and percentage changes from Baseline at Week 12 of the following:
 - ALT, AST, bilirubin (total, direct), and GGT
 - Total cholesterol, HDL cholesterol, LDL cholesterol, and triglycerides
 - C4 and serum bile acids
 - Bile-mediated absorption as measured by fat-soluble vitamins and fecal fat content
- Evaluate changes in pruritus and fatigue.
- Compare the incidence and severity of IBD-associated intestinal symptoms.
- Compare the incidence and severity of acute cholangitis during the study period.
- Evaluate the exposure of 1 mg and 3 mg of NGM282 in patients with PSC.
- Compare the dose-related changes in safety, tolerability, and pharmacodynamic (PD) parameters.

Exploratory PD Objectives:

- [REDACTED]
[REDACTED]
[REDACTED]
[REDACTED]

4 STUDY DESIGN

This is a multiple-center, randomized, double-blind, placebo-controlled, parallel-group study of NGM282 when administered for 12 weeks as a daily subcutaneous (SC) injection in patients with PSC. Approximately 60 subjects will be randomized across approximately 40–45 sites worldwide.

Patients will sign the Informed Consent Form at or prior to the Screening Visit and will undergo screening assessments to verify eligibility for the study (up to 6 weeks). Patients to be studied will have confirmed PSC as defined by an elevated ALP and either liver histology or cholangiography consistent with PSC. The presence of IBD is allowed as well as treatment with a stable regimen of biologic, immunosuppressant, or systemic corticosteroid therapy. UDCA therapy is allowed at stable doses for at least 12 weeks and < 27 mg/kg/day. Patients with decompensated cirrhosis, cholangiocarcinoma (diagnosed or suspected), acute cholangitis, or recently placed bile-duct stents will be excluded from this study. All subjects with concomitant IBD will be required to have had a colonoscopy within 12 months of Screening with no evidence of dysplasia. All subjects will undergo MRCP at Screening.

On Day 1, subjects will be randomized into one of the three treatment arms (NGM282 1 mg, NGM282 3 mg, or placebo) in a 1:1:1 ratio. The randomization will be stratified according to concurrent UDCA or no-UDCA status to ensure an even distribution across the three groups. Study-drug SC self-administration instructions and training will be provided to the subjects and a weekly study-drug kit will be dispensed. Treatment assignment will be blinded to the sites, subjects, Sponsor, and Medical Monitor throughout the study period.

The first dose (Day 1) and doses at Weeks 1, 2, 4, 8, and 12 will be self-administered in the clinic, with all other doses through Week 12 self-administered at home. Self-administration should occur at approximately the same time in the morning for every dose in both the clinic and at home.

Subjects will return to the clinic on Weeks 1, 2, 4, and 8 for on-treatment assessments and to receive weekly study-drug kits. Week 12 will be the End of Treatment (EOT) clinic visit. Subjects will return to the clinic at Week 16 (or 4 weeks after last dose) for an End of Study (EOS) follow-up visit.

4.1 STUDY STOPPING CRITERIA

The entire study may be discontinued at the discretion of the Sponsor based on the occurrence of the following:

- Adverse events (AEs) with respect to their nature, frequency, severity, and/or duration
- Medical or ethical reasons affecting the continued performance of the study
- Difficulties in the recruitment of patients
- Cancellation of drug development

The entire study will be discontinued by the sponsor if there are three or more related Grade 3 TEAEs of the same Common Terminology Criteria for Adverse Events (CTCAE) category.

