5.3 DISCONTINUATION OF STUDY TREATMENT IN AN INDIVIDUAL SUBJECT

Study treatment will be discontinued if any of the following CTCAE categories or abnormal elevations in liver function tests occurs on-treatment:

- Any Grade 3 TEAE related to study drug
- Any Grade 4 or higher TEAE
- Elevation of ALT **and** total bilirubin > 2 times above subject-specific baseline value calculated using the median of the Screening and Day 1 value
 - ALT, AST, and total bilirubin must be re-tested within 72 hours.
 - Subjects with persistent elevations should be discontinued from treatment, independent of whether or not they are symptomatic.
- Elevation of ALT > 2 times above subject-specific baseline
 - ALT, AST, and total bilirubin must be re-tested within 72 hours.
 - Subjects with persistent elevations who are asymptomatic may continue treatment under protocol-defined *close observation* criteria.
 - Subjects with persistent elevations who are symptomatic must discontinue treatment.
 - Subjects continuing treatment under *close observation* should implement study procedures and assessments as part of the study conduct:
 1. Repeat liver enzyme and serum bilirubin tests two or three times weekly. The frequency of retesting can decrease to once a week or less if abnormalities stabilize or the trial drug has been discontinued and the subject is asymptomatic.
 2. Repeat additional tests to evaluate liver synthetic function (e.g., INR, direct bilirubin) as appropriate.
 3. Obtain a detailed history of symptoms and prior or concurrent diseases.
 4. Obtain a history of concomitant drug use (including nonprescription medications and herbal and dietary supplement preparations), alcohol use, recreational drug use, environmental toxin exposure, and special diets.
 5. Rule out acute viral hepatitis and other acute or chronic hepatobiliary diseases.

Dose reductions or increases are not allowed as part the study conduct.

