Medication overdose may have occurred when an additional dose of a medication is known or suspected to have been taken (accidentally or intentionally) or when the dose administered exceeds the dose mandated by the protocol. An overdose can involve any study medication and should be reported whether or not there is an associated AE. An overdose is only considered an SAE if any of the defined criteria are met. Associated AEs should be recorded and assessed in the standard manner defined by the protocol. In cases of a discrepancy in drug accountability, an overdose will only be established when it is clear the subject has taken an extra dose or the investigator has reason to suspect additional doses were taken.

The PI will rate the severity of AEs using the CTCAE v4.03. Each CTCAE v4.03 term is a Medical Dictionary for Regulatory Activities (MedDRA) Lowest Level Term (LLT). The CTCAE displays Grades 1–5 with unique clinical descriptions of severity for each AE. Not all Grades are appropriate for all AEs. Therefore, some AEs are listed with fewer than five options for Grade selection. Grade 5 (Death) is not appropriate for some AEs and, therefore, is not an option.

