8.10.9 Interim Analysis

An unblinded interim analysis (IA) will be conducted when approximately 24 subjects (a minimum of 8 subjects per arm) have completed the Week 12 visit. At the IA, the evidence regarding the safety and efficacy of NGM282 in the PSC indication will be assessed, in order to evaluate the appropriateness of continuing the study.

A separate SAP for the IA will be generated, describing the conduct of the IA in detail.

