10.7 DATA MONITORING COMMITTEE

A Data Monitoring Committee (DMC) will be established in order to protect subject welfare, preserve study integrity, and provide recommendations as needed regarding study conduct. The DMC will be comprised of two external liver disease clinical experts as well as a statistician and a medical team member from the sponsor. The DMC will meet at predefined time points and on an as-needed basis based on enrollment, treatment milestones, and safety. Formal minutes and recommendations will be provided by the DMC to the sponsor regarding additional data requests and the continuation of the conduct of the study as outlined in the current protocol. The DMC will operate under the guidance of an agreed-upon charter.

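### The mandatory study-stopping rule in Protocol 4.1 counts related Grade 3 events only, so related Grade 4 or 5 events of the same CTCAE category do not count towards it

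*Protocol*

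**What the plan says.** Protocol section 4.1 has two parts. The first is discretionary: the sponsor may stop the study on several grounds, one of which is "Adverse events (AEs) with respect to their nature, frequency, severity, and/or duration". No threshold is attached. The second part is binding. It obliges the sponsor to end the whole study upon "three or more related Grade 3 TEAEs of the same Common Terminology Criteria for Adverse Events (CTCAE) category". This is the only mandatory study-level stop in the documents supplied.

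Section 5.3 sets triggers for stopping treatment in an individual subject. It lists "Any Grade 3 TEAE related to study drug" and, as a separate item, "Any Grade 4 or higher TEAE". The second has no relatedness condition.

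Section 7.1 grades adverse events by CTCAE v4.03 on five levels and notes that "Grade 5 (Death) is not appropriate for some AEs and, therefore, is not an option".

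Two other provisions bear on stopping. Section 8.10.9 plans one unblinded interim analysis, when about 24 subjects have completed Week 12, "in order to evaluate the appropriateness of continuing the study". Section 10.7 sets up a data monitoring committee that will "provide recommendations as needed regarding study conduct". Neither section states a grade-based threshold, and the SAP text supplied contains no stopping rule.

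**The concern.** A safety stopping rule should never become easier to satisfy when events are milder. This one does. If one of three related Grade 3 events had instead been Grade 4, the binding condition would no longer be met, although the safety picture is worse.

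The rule matters because it is where the sponsor commits itself in advance. Everything else at study level rests on judgement, and the sponsor's own judgement is made blind to treatment assignment (Protocol section 4). As written, the commitment covers the less severe pattern and leaves the more severe ones to discretion, with no reason given.

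The SAP shows one way this could arise. Its section 8.1.3 summarises TEAEs by maximum CTCAE grade. If the stopping count used the same convention (the documents do not say that it does), an event that began as Grade 3 and worsened to Grade 4 would drop out of the count, and deterioration would move the study away from a mandatory stop.

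**Working it through.** The plan gives no trigger probability or other operating characteristic for this rule, so there is no figure to reproduce. The check is by counting, followed by an illustration.

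**1. The two readings.** Let g3 be the number of related Grade 3 TEAEs in one CTCAE category and g45 the number of related Grade 4 or 5 TEAEs in that category.

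- As written: stop if g3 ≥ 3.
- With 'or higher': stop if g3 + g45 ≥ 3.

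| g3 | g45 | As written | With 'or higher' |
|---|---|---|---|
| 3 | 0 | stop | stop |
| 2 | 1 | no stop | stop |
| 2 | 5 | no stop | stop |
| 0 | 3 | no stop | stop |
| 0 | 10 | no stop | stop |

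**2. Grade patterns for exactly three related events.**

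- Grades 3, 4 or 5 possible: C(3+3−1, 3) = C(5,3) = 10 unordered combinations. Only (3,3,3) has three Grade 3 events, so 1 of 10 meets the rule and 9 do not.
- Grades 3 or 4 only (terms with no Grade 5, section 7.1): C(2+3−1, 3) = C(4,3) = 4 combinations. Again 1 meets the rule and 3 do not.
- With 'or higher': 10 of 10 and 4 of 4 meet it.

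Every pattern that fails the rule as written is more severe than the one that meets it. These counts give each pattern equal standing and say nothing about how likely any of them is.

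**3. Illustration with assumed rates.** The documents give no rates for related Grade 3 or higher events, so the rates below are assumptions. Suppose each subject has at most one related event in the category, with probability p3 of Grade 3 and p45 of Grade 4 or 5. The trigger probability is

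P(X ≥ 3) = 1 − Σ (k = 0 to 2) C(n,k) p^k (1−p)^(n−k),

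with p = p3 as written and p = p3 + p45 with 'or higher'.

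For example, with n = 40 and p = 0.05: 1 − (0.1285 + 0.2706 + 0.2777) = 0.323.

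Two values of n are shown. About 40 subjects receive NGM282 (two of three arms, 60 × 2/3). About 60 are randomised in all; relatedness is judged blind and section 4.1 is not limited to the active arms, so the rule applies to everyone. The n = 60 columns assume the same rates in all arms.

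| p3 | p45 | n = 40, as written | n = 40, 'or higher' | n = 60, as written | n = 60, 'or higher' |
|---|---|---|---|---|---|
| 5% | 0% | 0.323 | 0.323 | 0.583 | 0.583 |
| 5% | 1% | 0.323 | 0.433 | 0.583 | 0.706 |
| 5% | 2.5% | 0.323 | 0.586 | 0.583 | 0.837 |
| 5% | 5% | 0.323 | 0.777 | 0.583 | 0.947 |
| 2.5% | 2.5% | 0.078 | 0.323 | 0.190 | 0.583 |
| 0% | 5% | 0.000 | 0.323 | 0.000 | 0.583 |

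At a fixed Grade 3 rate, the 'as written' columns do not move with the Grade 4/5 rate. In the rows where the total rate is 5%, shifting events from Grade 3 to Grade 4/5 takes the trigger probability at n = 40 from 0.323 to 0.078 to 0.000.

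**The case against.** **Section 5.3 does not prove intent.** It needs two lines because relatedness is required for Grade 3 and not for Grade 4 or higher; a single 'Grade 3 or higher' line could not say that. So the split does not show that the authors meant to exclude higher grades in 4.1, and they probably did not. This is fair. But the finding rests on what 4.1 says. Section 5.3 adds only that the protocol writes 'or higher' where that is meant.

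**Severe events are not ignored.** Sections 7.3 and 7.3.1 require SAEs to be reported within 24 hours, with immediate notification of fatal or life-threatening ones. Fatal or life-threatening SUSARs go to regulators within 7 days. The committee can meet as needed on safety grounds, any Grade 4 or higher TEAE ends that subject's treatment, and the sponsor may stop the study because of severity. All of this stands and lowers the practical risk. None of it is a mandatory study-level stop, and section 5.3 leaves the other subjects on treatment.

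**The pattern count is not a measure of risk.** Correct. It shows the rule's logic, not how often the gap would matter, and the probabilities above rest on assumed rates.

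**The amended rule would still need three events.** Two related deaths would not trigger it. That is true, and a lower threshold for Grade 4 and 5 is a separate clinical decision. It is no reason to keep the present reversal.

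**Conclusion.** The concern holds. The only mandatory study-level stop in the documents counts related Grade 3 events and nothing above them. For three related events in one category it is met by 1 of 10 grade patterns (1 of 4 where Grade 5 does not exist), and that pattern is the mildest.

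The conclusion depends on reading section 4.1 literally and on the absence of any text elsewhere that extends the count. The DMC charter and the text of SAP section 9 are not available, so a threshold set there cannot be ruled out. No event rate is needed for the conclusion.

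The cause is most likely a drafting omission. Sections 4.1 and 5.3 can both be followed in practice, and the endpoints and efficacy analysis are untouched. Because this is a subject-protection rule that runs the wrong way with severity, it should be corrected.

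**What to change.** Reword the binding sentence in Protocol section 4.1 so that the count is of three or more related TEAEs of Grade 3 or higher in the same CTCAE category. When making the change, the sponsor may also consider whether related Grade 4 or 5 events warrant a lower number of their own.

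The text change is two words, and data collection and analysis are unaffected. It does need a formal amendment: Protocol section 10.1 requires written approval from the sponsor, the investigator and the ethics committee for changes affecting subject safety, across about 40–45 sites. The chance of a mandatory stop rises, by an amount that depends on the unknown Grade 4/5 rate; it is unchanged if no such events occur. Any added stops come only from related events more severe than those the rule already counts.

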5 SUBJECT SELECTION

5.1 INCLUSION CRITERIA

Patients who meet the following criteria may be included in the study:

1. Males and females between 18 and 75 years of age inclusive who are able to comprehend instructions and follow the study procedures, and are willing to sign an Informed Consent Form (ICF).
2. Confirmed diagnosis of PSC based any **two** of the following three criteria:
 - a. Historical evidence of an elevated ALP > ULN from any laboratory
 - b. Liver biopsy consistent with PSC
 - i. Patients with small-duct PSC on liver biopsy must also have a concurrent diagnosis of IBD
 - c. Abnormal cholangiography consistent with PSC as measured by MRCP, ERCP, or percutaneous transhepatic cholangiography
3. Subjects must have certain additional laboratory parameters in specified ranges at Screening, as follows:
 - a. ALP > 1.5 × ULN
 - b. Total bilirubin ≤ 2.5 mg/dL
 - c. ALT and AST < 5 × ULN
 - d. Serum creatinine < 2 mg/dL or creatinine clearance > 60 mL/min by Cockcroft-Gault calculation
 - e. Platelets ≥ 100 K/uL
 - f. International Normalized Ratio (INR) ≤ 1.3 (in the absence of warfarin or other anticoagulant therapy)
 - g. Carbohydrate antigen 19-9 (CA19-9) ≤ 130 U/mL
 - i. Patients with a CA 19-9 > 130 U/mL may be enrolled if they have two results a minimum of 4 weeks but not greater than 1 year apart and not more than 50 U/mL difference between the two results
4. Patients taking UDCA will be allowed to enroll if meeting the following criteria:
 - a. Total daily dose of < 27 mg/kg/day
 - b. Minimum of 12 weeks of treatment
 - c. No significant dosage changes during 8 weeks prior to Screening
 - d. Minimum of 12-week washout period prior to Screening if UDCA is stopped

5. Patients with concomitant IBD are allowed to enroll upon meeting the following criteria:
 - a. A colonoscopy within 12 months of Screening with no evidence of dysplasia
 - b. No episode of an IBD flare or IBD flare-related bloody diarrhea within 6 months of Screening and through Day 1
 - c. Stable regimen of biologic treatments, immunosuppressive, or systemic corticosteroids (< 10 mg/day) for > 12 weeks prior to Screening and through Day 1
 - i. Vedolizumab is an excluded biologic treatment
6. Female patients are eligible for the study if they meet the following criteria:
 - a. Are not pregnant or nursing
 - b. Of non-childbearing potential defined as women who have had a hysterectomy, bilateral oophorectomy, medically documented ovarian failure, or are documented postmenopausal (follicle-stimulating hormone > 40 mIU/mL)

OR

Of childbearing potential defined as including women < 55 years of age with 2 years of amenorrhea and **both** the following criteria:

- i. Both a negative serum pregnancy test at Screening and urine pregnancy test prior to Randomization
- ii. Correct and consistent use of one of the following methods of birth control in addition to a male partner using a condom from Screening to 30 days after the last dose of study drug:
 1. hormone-containing contraceptive
 2. intrauterine device with a failure rate < 1% per year
 3. cervical cap or diaphragm with spermicidal agent
 4. tubal sterilization
 5. vasectomy in male partner

7. Male subjects must agree to consistently and correctly use a condom in combination with one of the above methods of birth control from date of consent to 30 days after the last dose of study drug.
8. Subjects must be able to comply with the SC self-administration instructions for study drug and be able to complete the study schedule of procedures.

